Multicenter randomized controlled trial of vitamin K1 in the treatment of spontaneous intracerebral hemorrhage

1 Background

1.1 spontaneous intracerebral hemorrhage

1.1.1 Epidemiological of cerebral hemorrhage

Cerebral hemorrhage is a kind of acute onset, rapid change, serious disease, which accounts for about 10%-25% of cerebrovascular disease, disability rate and fatality rate were 70%-80%, 38%-43%, the recurrence rate was about 1 1.8%-11%. Hypertension and amyloid cerebrovascular disease are the main causes of primary spontaneous intracerebral hemorrhage, and hypertension is the most common risk factor for intracerebral hemorrhage. Cerebral hemorrhage not only has a serious impact on patients, but also brings heavy burden to society and family. The treatment of cerebral hemorrhage is complicated , which is one of the stroke which is proved by evidence-based medicine to be effective. Standardized treatment and effective integrated management can significantly reduce the fatality rate and improve the outcome of intracerebral hemorrhage.

Delayed cerebral hemorrhage is one of the important reasons for the aggravation of cerebral hemorrhage . The amount of hematoma in patients with intracerebral hemorrhage is closely related to the secondary injury of nerve function, which directly affects the prognosis of patients. Delayed cerebral hemorrhage is closely related to coagulation dysfunction. The prevention of delayed hemorrhage is an important part in the treatment of cerebral hemorrhage. The blood coagulation is initiated immediately after Acute intracerebral hemorrhage, and the coagulation process is divided into three stages: prothrombin complex formation, prothrombin activation, and fibrin formation. Synthesis of Coagulation factor FX, F II, F VII and F IX are dependent on vitamin K1. Vitamin K1 can cause the formation of prothrombin complex, clot solid, effectively blocking the vascular rupture, so that the amount of bleeding decreased. However, while controlling bleeding, the risk of thrombosis may be induced, and how to effectively control bleeding and avoid thrombosis is often a clinical problem.

1.2 Introduction of vitamin K1 injections

Vitamin K1 is an essential substance in the synthesis of prothrombin in the liver and can cause coagulation disorders when lacking. When the lack of prothrombin in the blood, blood coagulation will appear slow, then add appropriate amount of vitamin K1 can promote liver synthesis of prothrombin, play a role in hemostasis. Vitamin K1 as pharmaceutical formulations, applied to low thrombin disease, vitamin K1 deficiency, the prevention and treatment of neonatal hemorrhage, obstructive jaundice, biliary fistula, chronic diarrhea in clinic, Hypoprothrombinemia caused by coumarin and sodium salicylate etc.. Vitamin also has the effect of relieving pain and relieving bronchospasm, and has obvious effect on colic caused by visceral smooth muscle, colic, spasm of bile duct and spasm of intestine. Vitamin K1 can also be used as an additive for multidimensional foods and livestock feed.

Vitamin K1 indications: 1, low blood coagulation: intramuscular or deep subcutaneous injection, each time 10mg, 1-2 times a day, within 24 hours the total amount of not more than 40mg. 2, prevention of neonatal hemorrhage: 12-24 hours before delivery, intramuscular injection or slow intravenous injection 2 - 5mg. 0.5-1mg can also be injected intramuscularly or subcutaneously after birth, and can be repeated after 8 hours. 3, this product is used in patients with severe static injection, the speed of medication should not exceed 1mg/. 4, can be used for chronic poisoning caused by brodifacoum. Specific usage: (1) intravenous injection of 5 mg / kg vitamin K1, such as the need to repeat 2-3 times, each time interval of 8-12 hours. (2) oral administration of 5 mg / kg of vitamin K1 for 10-15 days. (3) intravenous injecting 200 ml of lemon acidified blood.

1.3 Possible risks

Adverse reactions of vitamin K1: occasionally allergic reactions. Mainly occurs when the intravenous injection is too fast, more than 5mg/ minutes can cause facial flushing, sweating, bronchospasm, tachycardia,

hypotension, etc., serious allergic reactions may endanger life. Intramuscular injection can cause redness and swelling. The newborn may suffer from hyperbilirubinemia, jaundice and hemolytic anemia after the use of the product.

.1.4. Benefits

Cerebral hemorrhage is a common disease in Department of neurosurgery. It is an important measure to reduce the mortality and disability rate in the acute stage. Vitamin K1 may reduce the risk of rebleeding in patients with intracerebral hemorrhage, and the amount of brain bleeding is directly related to prognosis. Effectively reduce the amount of intracerebral hemorrhage, improve the prognosis, reduce the length of stay, reduce the time of admission to ICU and reduce the mortality.

2 Test purpose

The effectiveness and safety of vitamin K1 were mainly targeted at patients with cerebral hemorrhage (non aneurysm or vascular malformations, rupture, bleeding). To observe whether vitamin K1 can effectively avoid the increase of cerebral hemorrhage and improve the prognosis.

3 Test design

The study included spontaneous hypertensive intracerebral hemorrhage at super tentorium of cerebellum patients as the research object, to exclude cerebral aneurysms or cerebral hemorrhage, venous malformation of abnormal liver function, taking anticoagulants or antiplatelet drugs in patients. The study was divided into the experimental group and the control group, and a multicenter randomized controlled trial was conducted. In the use of a etamsylate intravenous infusion of 0.5g of patients admitted to hospital within 8 hours later, the experimental group in the incidence of cerebral hemorrhage within 2 days after the daily intravenous infusion of vitamin K1 20mg, the control group received intravenous saline, all patients were no longer use other hemostatic agents. The efficacy and safety of vitamin K1 in the early onset of cerebral hemorrhage were assessed by the observation between two groups.

A randomized, single blind, positive / placebo parallel control, multicenter, clinical trial design was used. The treatment lasted for 2 days and followed up for 6 months.

4 Subjects recruited and exited

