4.3 Exclusion criteria

1) CT scan and irregular lobulated hematoma, such as intraventricular hemorrhage (because no accurate measurement of bleeding);

2) Severe liver disease or impaired liver function;

3) Pregnant or lactating women;

4) The usage of anticoagulation or antiplatelet aggregation drug history (including cilostazol, aspirin, dipyridamole, heparin, low molecular weight heparin, hirudin, dabigatran, rivaroxabanand warfarin);

5) Non informed consent.

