6.1.4 Route of administration

Basic treatment: all subjects according to the routine treatment of cerebral hemorrhage, the use of Phenol ethylamine intravenous 0.5g within 8 hours after admission, another program in accordance with the "Neurosurgery of Wang Zhongcheng", including the surgical removal of hematoma and drainage, conservative treatment, control of intracranial pressure, prevention of complications.

Test group:

Normal saline 100ml+Vitamin K1 20mg, Once a day, intravenous drip, two days in

hospital.

Control group:

Normal saline 102ml, Once a day, intravenous drip, two days in hospital.

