7.1 Test program evaluation

①Demographic data: age, sex, and ethnic group.

⁽²⁾History: ask for or collect current and past medical history based on existing medical records.

③Medication history: before taking the test, take the prescription or over-the-counter drugs, and record the generic name, daily total dose, usage and cause of use of the drug.
④The diagnosis of disease was confirmed by CT or MRI, and the amount of cerebral hemorrhage was calculated at the later stage (after the onset of the disease, the examination was not repeated).

⁽⁵⁾Physical examination: vital signs include body temperature (Ye Wen), respiration, heart rate, and blood pressure.

⁽⁶⁾Assessment of biological specimen collection and laboratory: collected blood and urine of Hematology, serum biochemistry, pregnancy test and laboratory examination, biological specimens from all participating units of the laboratory is responsible for collecting, processing, preservation and detection. Prior to the signing of the test drug, the clinical trial participant shall provide the bid with the normal reference range of the laboratory indicators. If there is any change during the test period, the applicant shall be promptly informed of the bid.

⑦Scale evaluation: mRS score.

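### Section 1.3 warns of life-threatening allergic reactions to vitamin K1, yet no entry or rejection criterion addresses known hypersensitivity to it, and the history in 7.1 has no allergy item.

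*Protocol*

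**What the plan says.** Protocol 1.3 lists allergic reactions first among the adverse reactions to vitamin K1. It qualifies them ("Mainly occurs when the intravenous injection is too fast", with a figure of more than 5 mg per minute) and adds that "serious allergic reactions may endanger life". Section 6.1.4 gives the test arm "Normal saline 100ml+Vitamin K1 20mg, Once a day, intravenous drip, two days in" hospital; the control arm receives saline alone.

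The exclusion list in 4.3 has five items:

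1. haematoma form ("CT scan and irregular lobulated hematoma, such as intraventricular hemorrhage"), on grounds of measurement;
2. "Severe liver disease or impaired liver function";
3. "Pregnant or lactating women";
4. a history of anticoagulant or antiplatelet drugs;
5. absence of consent.

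No catch-all or investigator-judgement item follows. Section 7.1 provides for staff to "ask for or collect current and past medical history based on existing medical records" and to record earlier medication by name, dose, use and reason. It has no field for drug allergy or past drug reactions, and nothing in it feeds back into eligibility on this point.

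**The concern.** The protocol names a potentially fatal reaction to its own study drug, gives that drug by the route it associates with the reaction, and leaves the question of known allergy out of its eligibility rules. A site that followed the text exactly could randomise a patient whose records show a vitamin K1 allergy.

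Two things are at stake. The first is the safety of that patient. The second is the comparison. Once a patient has been allocated, a careful clinician who learns of the allergy has a reason to stop vitamin K1 but no such reason to stop saline. Departures from treatment would then depend on the arm, which a criterion applied before randomisation prevents.

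**Working it through.** No formula governs this point, and the plan gives no figure to reproduce. The check is a reading of every place where the gap could have been closed.

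- **Inclusion, 4.2.** Six items are printed (1 and 3 to 7). Mentions of drug allergy: 0 of 6. The numbering skips item 2, so one criterion may have been lost or deleted.
- **Exclusion, 4.3.** Items 1 to 5, numbered without a gap. Mentions: 0 of 5.
- **Rejection, 4.4.** Three items. The first two work only through 4.2 and 4.3, and the third concerns missing visits. Since neither list covers allergy, 4.4 does not reach it. Mentions: 0 of 3.
- **Design summary, section 3.** It repeats exclusions for vascular causes, liver function and antithrombotic drugs. Allergy is not among them.
- **History, 7.1 and the flow chart in 7.5.** History is taken at D0, with no allergy item and no linked rule.
- **Exit criteria, 4.5.1, and adverse-event handling, 9.3 and 9.4.** These act on events after entry. They are not screening.

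Read together, these sections leave a patient with known vitamin K1 allergy who meets the other criteria eligible.

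**After allocation.** Section 6.1.1 describes single-blind administration by the investigators and does not say who is blinded. If the treating team knows the arm, a newly noticed allergy affects the vitamin K1 arm only. If it does not, the team would have to withhold treatment in both arms or break the code. In either case the patient becomes a protocol departure. SAP section 5(3) names the full analysis, per-protocol and safety sets but gives no membership rule that would settle where an allocated but untreated patient belongs. The arm-specific effect is my inference; the documents do not discuss it.

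**Size.** The documents give no prevalence of known vitamin K1 allergy. The working assumption is well under 1%, that is, from none to fewer than 1 in every 100 patients screened. I found no target sample size in either document, so this cannot be turned into a firm count.

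**The case against.** The strongest reply is that 1.3 presents the risk as chiefly one of injection speed. The test dose is 20 mg in a drip. At the 5 mg per minute mentioned in 1.3, that dose would take 20 ÷ 5 = 4 minutes, so the drip would have to run in under 4 minutes to pass that figure. This is fair and lowers the expected frequency of reactions. It does not close the gap: 1.3 says mainly, not only, and neither 6.1.3 nor 6.1.4 states an infusion rate. The missing rate is a separate matter.

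A second reply is that history is taken at D0 by asking or from existing records, so a known allergy may well surface even when the patient cannot speak. That also stands, and it means that family consent is not a strong argument here. But no rule says what to do with the information.

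Third, the list in 4.3 is not described as closed, text may be missing from 4.2, and the kit instructions mentioned in 6.1.3 are not available to us. These are real limits on certainty. Still, 4.3 is numbered without a gap and has no catch-all, and kit instructions would apply only after allocation.

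Finally, this is an omission rather than a contradiction between two rules. That is correct. The need is for the eligibility section to answer a risk that the background section raises.

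**Conclusion.** The point holds for hypersensitivity. As written, the eligibility rules admit a patient with known allergy to the study drug, although 1.3 describes serious reactions as potentially fatal. It probably affects very few patients, on the assumption stated above, and no effect on the primary outcome or on any estimate has been shown. The case for acting is the seriousness of the event and the very low cost of prevention.

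A reader might infer a parallel gap for thrombosis, because 1.1.1 warns that "while controlling bleeding, the risk of thrombosis may be induced" and 4.3 does not name existing thrombosis. The reader might go on to argue that thromboses present at entry would dilute the safety comparison. The documents do not support that:

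- Section 1.1.1 speaks of inducing thrombosis. It does not call existing thrombosis a bar to treatment.
- Exclusion 4 already removes patients whose thrombosis was treated with anticoagulant or antiplatelet drugs.
- History is taken at D0, and the damaged flow chart appears to mark complications at all seven time points, D0 included.
- Section 9.1 limits adverse events to those after drug, 9.3.2 requires the time of occurrence, and 9.6 grades causality by the sequence of drug and event.

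Events present at entry can therefore largely be separated from new ones. Any figure for a diluted risk ratio would rest on prevalence and event rates that the documents do not contain.

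**What to change.** Reconcile 4.3 with 1.3 so that known hypersensitivity to the study drug is dealt with at eligibility, before randomisation. The clinical team should set the wording and scope. Add an allergy-history item to the D0 history in 7.1 and to the case report form, so that the criterion has data behind it.

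The cost is one extra history field, a short change to the eligibility text and, on the assumption above, at most a handful of patients becoming ineligible. No additional test is needed.

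Optionally, a named D0 field for existing thrombosis would make explicit what the D0 history and complications record already appear to capture. It is a matter of clarity and not a condition of the main change.

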4.1 Diagnostic criteria

4.1.1 Diagnosis of cerebral hemorrhage

Referring to "Surgery" edited by Chen Xiaoping, and published in 2011 by people's Medical Publishing house.

4.1.2 Treatment methods

According to "Neurosurgery of Wang Zhongcheng", conventional cerebral hemorrhage treatment.

4.2 Inclusion criteria

1) Patients with spontaneous intracerebral hemorrhage (enhanced by cerebral arterial CT or cerebral angiography confirmed rupture of non aneurysm or arteriovenous malformation);

3) Age 18-65 years, male or not pregnant female;

4) GCS score at admission;

5) Head CT or MRI examination confirmed cerebral hemorrhage at super tentorium of cerebellum and the amount of bleeding in 10ml-45ml (Duotian formula to calculate the hemorrhage volume);

6)During the hospitalization, no urokinase and other hemostatic drugs were used except for the use of K1 and vitamin D in the project;

7) Informed consent form signed by the patient's family.

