4.4 Rejection standard

1) The subjects failed to meet the inclusion criteria and were mistakenly included in the trial.

2) The subjects met either of the exclusion criteria.

3) No record of any further visits.

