4.5 Exit test standard

4.5.1 The researchers decided to quit

1)During the clinical trial, the subjects experienced other complications, complications,

or special physiological changes, and were not allowed to continue the experiment..

2) Serious adverse events and important adverse events, it is not appropriate to continue to accept the test.

3) The subjects had poor compliance.

4) The test process meets the rejection criteria.

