4.5.3 Withdrawal case management

In the case of the withdrawal from the trial, the researchers should actively take measures to complete the final examination as soon as possible to analyze the efficacy and safety. All trial cases should be completed in the case report form and the reasons for the withdrawal.

5 Suspension test standard

The discontinuation test means that the clinical trials have not been completed by the end of the program. The purpose of the suspension test is to protect the rights and interests of the subjects, to ensure the quality of the test and to avoid unnecessary economic losses. Standard for discontinuation of a test:

1) serious safety problems in the test, should promptly stop the test.

2) The trial found that the drug did not have clinical value and should discontinue trials, on the one hand, to avoid delaying the effective treatment of the subjects while avoiding unnecessary economic losses.

3) In the experiment, it was found that the clinical trial program had major errors and

it was difficult to evaluate the effect of the drug; or a well-designed design, which made important deviations in the implementation, and continued, it is difficult to evaluate the effect of the drug.

4) The applicant asked for a suspension (such as funding reasons, management reasons, etc.).

6 Treatment Plans

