7.5.2 No medication or treatment

During the period of medication and during the follow-up period, drugs that affect the efficacy of the regimen may not be used, such as antithrombotic or anticoagulant or hemostatic drugs.

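### Inclusion criterion 6 is judged on drugs given after randomisation, so with the rejection and exit rules it can remove patients for reasons related to outcome

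*Protocol*

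**What the plan says.** Protocol 4.2 item 6 is listed as an inclusion criterion: "During the hospitalization, no urokinase and other hemostatic drugs were used except for the use of K1 and vitamin D in the project".

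Protocol 4.4 item 1 gives as a ground for rejection: "The subjects failed to meet the inclusion criteria and were mistakenly included in the trial". Protocol 4.5.1 item 4 lets the researchers withdraw a patient when "The test process meets the rejection criteria". For withdrawn cases, 4.5.3 asks the researchers to "complete the final examination as soon as possible to analyze the efficacy and safety". It does not say that scheduled visits continue.

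The same kinds of drug are already restricted by a conduct rule. Protocol 7.5.2 says that, during medication and follow-up, "drugs that affect the efficacy of the regimen may not be used, such as antithrombotic or anticoagulant or hemostatic drugs".

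The SAP, section 5(3), names the PPS, FAS and SS but defines none of them and does not say which is primary. It leaves deviating cases to be settled after review of how the trial was run. SAP 2(1) applies LOCF to important data but not to secondary indices.

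All patients also receive a background drug. Section 6.1.4 describes it as "the use of Phenol ethylamine intravenous 0.5g within 8 hours after admission", and section 3 gives it another name and adds that "all patients were no longer use other hemostatic agents".

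**The concern.** An inclusion criterion should be decidable before randomisation. Item 6 can be breached only by what happens during the stay, which takes in both treatment days and most or all of the volume assessments. Because 7.5.2 already restricts haemostatics, item 6 adds no control over drug use. Its only added effect is to turn a later deviation into a question of eligibility.

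A haemostatic newly given after admission is plausibly a response to bleeding. Haematoma volume is a main outcome in section 8 of the Protocol, and section 1.4 expects vitamin K1 to reduce rebleeding. If patients leave the trial or the analysis because they were given such a drug, the patients who remain are selected on something close to the outcome. The comparison is then no longer between the groups as randomised. The 6-month mRS, on which the SAP bases its superiority conclusion, is exposed in the same way.

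**Working it through.** **The route through the text**

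1. Item 6 covers the hospital stay, so a patient who is eligible at randomisation can breach it later.
2. 4.4 item 1 makes failure of an inclusion criterion a ground for rejection, with a qualifier about mistaken inclusion (see the objection).
3. 4.5.1 item 4 applies the rejection criteria while the trial is running and leads to exit.
4. 4.5.3 brings the final examination forward and is silent on the remaining CT scans and on the mRS at 1 and 6 months.
5. No SAP sentence says these patients are kept as randomised. Even if they stay in the FAS, early exit with LOCF could put an earlier value in place of a later volume or the 6-month mRS. If the index counts as secondary, the value would simply be missing.

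**How much this could matter**

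The documents give no rebleeding rate, effect size, SD or sample size, so there is no figure of the plan to reproduce. Every input below is an assumption:

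- Risk of haematoma expansion p: 0.30 control, 0.20 vitamin K1.
- Mean growth 15 ml with expansion and 0.5 ml without, so the excess is 15 − 0.5 = 14.5 ml.
- A share q of expanders is given a barred drug and removed. Non-expanders are not removed.

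Among patients kept, the expander share is p(1 − q)/(1 − pq). The arm difference (K1 minus control) is the difference in these shares × 14.5 ml. With nobody removed it is (0.20 − 0.30) × 14.5 = −1.45 ml.

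With equal q in both arms, the fraction of the true difference retained is (1 − q)/[(1 − 0.30q)(1 − 0.20q)]:

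| q | removed, control / K1 (pq) | fraction retained | difference | lost |
|---|---|---|---|---|
| 0.10 | 3% / 2% | 0.90/(0.97 × 0.98) = 0.947 | −1.37 ml | about 5% |
| 0.25 | 7.5% / 5% | 0.75/(0.925 × 0.95) = 0.853 | −1.24 ml | about 15% |
| 0.50 | 15% / 10% | 0.50/(0.85 × 0.90) = 0.654 | −0.95 ml | about 35% |
| 0.75 | 22.5% / 15% | 0.25/(0.775 × 0.85) = 0.380 | −0.55 ml | about 62% |

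The retained fraction does not depend on the 14.5 ml, so the same percentages apply to mRS if expansion shifts it by a fixed amount. At an assumed 1.5 points per expansion, the true difference of −0.15 becomes −0.15 × 0.654 = −0.098 at q = 0.50.

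A harmful effect is also shrunk. With p = 0.30 control and 0.40 K1, 10% to 54% is lost for q = 0.25 to 0.75.

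**Removal that differs by arm** (control q, K1 q)

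- True effect present, 0.50 and 0.30: (0.14/0.94 − 0.15/0.85) × 14.5 = −0.40 ml.
- True effect present, 0.60 and 0.20: (0.16/0.96 − 0.12/0.82) × 14.5 = +0.29 ml, so the sign reverses.
- No true effect (p = 0.30 in both arms), 0.60 and 0.20: (0.24/0.94 − 0.12/0.82) × 14.5 = +1.58 ml.
- No true effect, 0.30 and 0.50: (0.15/0.85 − 0.21/0.91) × 14.5 = −0.79 ml.

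**No effect and equal removal:** the two shares are identical, so the difference stays at zero. At p = 0.30 and q = 0.25 to 0.75, 7.5% to 22.5% of each arm is lost without bias.

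**The case against.** The strongest reply is that 4.4 item 1 concerns patients who were mistakenly included. Someone given a barred drug on day 3 was not enrolled by mistake. SAP 5(1) also tabulates failed inclusion criteria separately from concomitant drug use, and 5(2) analyses concomitant drugs. SAP 5(3) speaks of imputing data for deviating cases, and 4.5.3 wants withdrawn cases examined so that they can be analysed. On this reading, barred drugs are ordinary deviations and nobody is dropped.

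Much of this stands. The route to removal is permitted by the text, not plainly ordered. But item 6 can be failed only by conduct during the stay, 4.5.1 item 4 applies rejection during the trial, and nothing settles which reading governs. It could be settled patient by patient after outcomes are seen.

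Four stronger readings are tempting, and the documents do not support them:

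- **Rejected patients are outside the FAS.** No sentence says so. The FAS is undefined, which is a gap and not an exclusion.
- **The rule removes patients because they rebled, and so biases the result.** No reason for giving a barred drug is stated. The supportable wording is that it can bias, under the conditions shown.
- **The investigators applying the rule know the arm.** Sections 3 and 6.1.1 say only single blind and do not say who is blinded. The sign reversal and the false effects need removal that differs by arm.
- **Every patient fails item 6, because the background drug is not exempted.** That is the literal reading. But the exemption for vitamin D appears nowhere else and the background drug has two names, so a translation fault is possible. Section 3 also sets that drug apart from other haemostatics. This is a matter to reconcile, not evidence that removal is discretionary.

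**Conclusion.** The point holds as a defect in the rules. An eligibility criterion is judged after randomisation, the rejection and exit sections give a route from it to withdrawal, and the SAP has no rule that keeps such patients in follow-up and analysis.

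The size cannot be fixed from the documents. If barred drugs follow bleeding and vitamin K1 changes rebleeding, equal removal pulls the estimate towards no difference. The loss is small if few expanders are affected (about 5% of the effect at one in ten) and large if many are (about 35% at one in two). Bias without a true effect requires use or rejection to differ by arm. If neither condition holds, the cost is lost patients and precision only.

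It should still be corrected, because visits missed after an early exit cannot be recovered at analysis.

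**What to change.** - **Protocol 4.2:** remove item 6, so that eligibility rests only on facts known before randomisation. Leave concomitant drugs to section 7.5 (Concomitant medication and treatment).
- **Protocol 4.4 and 4.5.3, and SAP 5(3):** state that use of a barred drug after randomisation is a recorded protocol deviation that neither ends follow-up nor removes the patient from analysis. This concerns follow-up and analysis only. It says nothing about stopping study drug or about which drugs may be given.
- **SAP 5(3):** define the FAS as all randomised patients, analysed as allocated, with all measured volumes and mRS scores. Name it as the primary set and confine exclusions for barred drugs to the PPS.
- **Separately:** the drugs exempted in 4.2 item 6 and those barred in 7.5.2 must be reconciled with the background drug given to all patients under sections 3 and 6.1.4, including its two names.

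The cost is wording, plus the visits that withdrawn patients would otherwise have missed. The downside is that patients given other haemostatics stay in the main analysis and slightly dilute a pure drug effect. The PPS can still show the results without them.
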